### **ii. LIST OF ABBREVIATIONS**

Define all unusual or 'technical' terms related to the trial. Add or delete as appropriate to your trial. Maintain alphabetical order for ease of reference.

AE Adverse Event
AR Adverse Reaction
CA Competent Authority
CI Chief Investigator
CRF Case Report Form

CRO Contract Research Organisation

CTA Clinical Trial Authorisation

CTIMP Clinical Trial of Investigational Medicinal Product

CTU Clinical Trials Unit

**DMC Data Monitoring Committee** 

**DSUR Development Safety Update Report** 

EC **European Commission** 

**EMEA European Medicines Agency** 

EU **European Union** 

**EUCTD European Clinical Trials Directive EudraCT** European Clinical Trials Database

**EudraVIGILANCE** European database for Pharmacovigilance

**GCP Good Clinical Practice** 

**GMP Good Manufacturing Practice** 

ΙB Investigator Brochure **ICF** Informed Consent Form

**ICH** International Conference on Harmonisation of technical

requirements for registration of pharmaceuticals for human

use.

**IMP Investigational Medicinal Product** 

**IMPD** Investigational Medicinal Product Dossier

**ISF** Investigator Site File (This forms part of the TMF)

International Standard Randomised Controlled Trials **ISRCTN** 

Number

MA Marketing Authorisation

**MHRA** Medicines and Healthcare products Regulatory Agency

MS Member State

NHS R&D National Health Service Research & Development

**NIMP** Non-Investigational Medicinal Product

ы Principal Investigator

PIC Participant Identification Centre PIS Participant Information Sheet

QA **Quality Assurance** QC **Quality Control** QP **Qualified Person** 

**RCT** Randomised Control Trial

REC Research Ethics Committee

SAE Serious Adverse Event
SAR Serious Adverse Reaction
SDV Source Data Verification

SOP Standard Operating Procedure

SmPC Summary of Product Characteristics

SSI Site Specific Information

SUSAR Suspected Unexpected Serious Adverse Reaction

TMF Trial Master File

TMG Trial Management Group
TSC Trial Steering Committee

		- At least 6/8 schools are successfully recruited, randomised and retained throughout the study
		- Participation rates at intervention and control schools retained in the trial are at least:
		60% of teacher-reported SDQ at baseline. 80% retained at follow-up.
		60% of child-report Stirling Wellbeing Questionnaire at baseline. 60% retained at follow-up.
		Any differences in the characteristics of the children with missing data on teacher report measures (when compared to those with complete data) are able to be handled successfully via statistical methods.
Secondary	n/a	n/a
Investigational Medicinal Product(s)	Outdoor Play and Learning (OPAL) play intervention for schools.	
Formulation, Dose, Route of Administration	18 month, mentor led programme, delivered in junior or primary schools.	

#### iv. FUNDING AND SUPPORT IN KIND

FUNDER(S)  (Names and contact details of ALL organisations providing funding and/or support in kind for this trial)	FINANCIAL AND NON FINANCIALSUPPORT GIVEN
UKRI	Financial support
University of Exeter	In kind support through covering staff time for health economics, trial management advice and statistics support.
Department of Health and Social Care	Excess treatment costs of paying for the OPAL programme all eight schools

#### v. ROLE OF TRIAL SPONSOR AND FUNDER

The funder has no role in the design or implementation of the trial; they fund the time for staff members and associated costs (e.g. travel to schools, dissemination costs etc.). The University of Exeter similarly has no role in the design or implementation of the trial but support staff time.

# vi. ROLES AND RESPONSIBILITIES OF TRIAL MANAGEMENT COMMITEES/GROUPS & INDIVIDUALS

[figure not shown]
There will be a Trial Advisory Group (TAG), which will include parents, teachers, academics and play professionals. The majority of members of the advisory board will be independent of the University of Exeter, UKRI and OPAL. The TAG will meet regularly to ensure all practical details of the trial are progressing well and working well and everyone within the trial understands them. Any issues that arise during the trial will be discussed with the TAG.

#### vii. Protocol contributors

The protocol has been written by [name], with support from [name]. The protocol was developed with input from experts in statistics ([name]), health economics ([name]) and trial design ([name]). The proposal has been influenced heavily by initial pilot work conducted at two primary schools by the above research team and colleagues [name] and [name] as well as student researchers who collected data in schools. Head teachers, school staff, parents and children have been involved in the development of the protocol, primarily through close working during the pilot stage and one to one interviews at the end of the research and intervention.

viii. KEY WORDS: School-based intervention, playtime intervention, play, mental health, recess, breaktimes

#### ix. TRIAL FLOW CHART

#### 1 BACKGROUND

Mental health problems are a leading cause of disease burden (1). The economic costs of mental ill health in England are estimated at £105.2bn per year. Pathways to mental health problems begin in childhood with emotional disorders such as anxiety having a particularly early onset (2). Emotional disorders are also the most common mental health disorders; affecting more than 250,000 primary school-aged children in England (3). To reduce mental ill health, prevention during childhood is key (4). Time outdoors is linked to improved wellbeing in children, which protects against poor mental health (5). Outdoor time provides children with a unique opportunity for boisterous, adventurous, active, child-led, play and there is increasing evidence that this type of play has positive effects on children's mental health (6). Despite this, opportunities for outdoor play are declining in and outside of schools. Given this, the proposed research will inform the feasibility of conducting a full Randomised Controlled Trial (RCT) of a school-based intervention to improve the quality of outdoor play in English primary/junior schools, as a route to reducing mental health problems and improving wellbeing and enjoyment of school.

Initial evidence supports school programmes that aim to improve outdoor play as beneficial for children's mental health and well-being. For example, Lavrysen et al. (5) gave school children opportunity to engage in child-led play, including exploring risks. Post-intervention, significant improvements were found in teacher ratings of children's self-esteem, conflict sensitivity and concentration. Other school programmes have introduced recycled materials for children to play with and found improvements in physical activity and cognitive development, but mental health has not been assessed.

In this research we will work with Outdoor Play and Learning (OPAL) who have created an intervention that aims to make playtimes better for children. The programme helps schools to provide excellent play for all children every day. It has been developed over 20 years with input from teachers, parents and children. Many primary schools have already done the programme and preliminary evaluations of OPAL have been positive, reporting increases in resilience and improvements in children's happiness and wellbeing (14, 15). There has not yet been a strong scientific assessment of how the OPAL programme affects children's mental health and wellbeing. Furthermore, the mental health outcomes of school-based outdoor play programmes have yet to be examined systematically. There is convincing evidence though from other contexts, such as hospitals, that child-led play can improve children's mental health and wellbeing (16, 17).

The OPAL programme provides participating schools with an experienced mentor who supports the school over the course of an 18-month period to change their playtimes (see later intervention section for more details). and setting goals for the programme, later sessions include a training session for staff where they learn about theory and practice in playwork. Playworkers are trained to create environments to ensure play opportunities are as diverse and inclusive as possible, to observe, reflect and analyse the play that is happening and to make changes to the environment if needed. The guiding principle underlying this approach is that where possible play should be freely chosen, child

led and intrinsically motivated. Often adults make choices about what children should play and set constraints and rules around children's play (e.g. 'lets play hide and seek, you hide l'Il count). Playwork training helps adults working with children to understand that their role is to create a playful environment and then to step back and allow children to lead the play. When children direct their own play, in a diverse environment they will naturally challenge themselves in their play in a way that is stretching but appropriate for them. The play programmes therefore increase adventurous play by working to provide children with more space and permission to lead their own play.

In addition, schools would be encouraged to introduce loose parts for play such as tyres and milk crates which give children more opportunity for creative, child-led play which may be adventurous in nature. Further sessions provided as part of the programme include what is called risk-reframing training for teachers and parents. During these sessions teachers and parents are taught how to implement the risk benefit approach recommended by the Health and Safety Executive (see https://www.hse.gov.uk/entertainment/childs-play-statement.htm). This approach requires adults to consider risks in the contexts of benefits rather than taking a risk minimisation approach; often a risk also provides a learning opportunity (benefit) and therefore the risk may be justified because of the benefits it offers. For example, a balance beam has a risk that a child will fall off and hurt themselves but it has the benefit of giving children an opportunity to practice balancing and to develop their balance skills. The final sessions focus on including play within school policies and documentation and ending the mentoring with future planning and goal-setting.

This current research will inform the feasibility of conducting a full Randomised Controlled Trial (RCT) of a school-based intervention to improve the quality of outdoor play in English primary/junior schools, as a route to reducing mental health problems and improving wellbeing and enjoyment of school.

#### 2 RATIONALE

In England, 1 in 6 children have a probable mental health disorder and over half a million children are referred to NHS mental health services per year (7). Government strategy and policy highlight that child mental health is an important, long-term issue (8) and that better prevention is required (9). Emotional problems such as anxiety are the most common disorders experienced in childhood and they predict long term mental health problems (10). They are therefore a crucial target for prevention.

There is substantial health inequality apparent in children's mental health problems; there is an overrepresentation of girls, children with special educational needs and children from low income families (3). As state primary schools have near universal coverage of children, prevention programmes delivered in schools have the potential to address these health inequalities as well as the sequalae of inequalities that occur as a result of having a mental health problem.

Prevention of anxiety and emotional problems more broadly typically involves CBT-based approaches, either targeted or universal, which teach children (or their parents) the principles of CBT. These approaches have had mixed success.

Recent theory proposes that adequate freedom to play may provide an opportunity for children to learn some of what would be targeted in a CBT-based prevention programme, such as adaptive coping styles, unbiased appraisal of physiological arousal and prevention of avoidance (Dodd & Lester, 2021). In support of this theory, initial research shows that children who spend more time playing outdoors and more time playing adventurously have fewer emotional problems (11). Despite this, children spend less time playing outdoors now than in previous generations (12) and the proportion of children playing with friends after school has also significantly declined (13). These changes mean that school playtime is an increasingly important opportunity for children to play outdoors. Since 1995 though, playtimes have decreased by 45 minutes per week and most schools focus on risk minimisation and containment during playtime (13).

This feasibility RCT focuses on reducing children's mental health problems via a programme designed to improve child-led outdoor play in schools. The Outdoor Play and Learning (OPAL) programme aims to harness playtimes to provide every child with access to rich outdoor play opportunities, as a route to decreasing inequality in access to outdoor play and, in doing so, reducing children's risk for mental health problems and increasing their wellbeing and enjoyment of school. The OPAL programme is established and has been implemented at many schools but only initial evaluations have been conducted, none of which would be considered a clinical evaluation (14).

The intervention will be delivered at school-level (with schools as study participants) and is therefore a universal intervention. The intervention delivery time, based on careful development by OPAL, is 18 months. Control schools will be asked to continue with usual practice at playtimes during this period, as this is considered least disruptive. Control schools will be given the intervention after the 18 month wait period. No children will be prevented from seeking support for their mental health during this period, as this falls within usual practice.

The aim of the research is to determine the feasibility of progressing to a cluster RCT of an outdoor play programme for primary/junior schools which aims to improve the quality of children's outdoor play as a route to decreasing children's risk for mental health problems and improving children's wellbeing and enjoyment of school.

### 2.1 Assessment and management of risk

Schools will be recruited after they have decided to complete the OPAL programme; they will not be asked to complete the programme as part of the research. This means that the risks of the research are low. There is a cost in terms of lesson time but we have evaluated this together with teachers and school leaders who advise that the disruption is minimal and the importance of the research justifies this time.

The OPAL programme involves training in risk benefit assessment and supports schools to provide opportunities for children to explore risk-taking. This means that there may be an increased in risky or adventurous play during playtimes (e.g. building dens, riding scooters, jumping onto and off tyres), and there may be an associated increase in injuries. The OPAL programme has been implemented in hundreds of schools and, anecdotally, schools report that injuries *decrease* when the programme is implemented. We therefore consider this to be a low probability risk. Furthermore, with the training that OPAL provide, school staff will be well prepared for identifying and stopping play that is considered dangerous.

This trial is categorised as:

Type A = No higher than the risk of standard medical care

#### 3 OBJECTIVES AND OUTCOME MEASURES/ENDPOINTS

### 3.1 Primary objective

The aim of this project is to determine the feasibility of progressing to a cluster RCT (with intervention and waitlist arms) of an outdoor play programme for primary/junior schools which aims to improve the quality of children's outdoor play as a route to decreasing children's risk for mental health problems and improving children's wellbeing and enjoyment of school.

No hypotheses are evaluated because this is a feasibility trial.

### 3.2 Secondary objectives

n/a

### 3.3 Outcome measures/endpoints

See table below.

### 3.4 Primary endpoint/outcome

The primary outcome for the full RCT will be teacher-reported scores on the Emotional Difficulties scale of the SDQ.

For the feasibility RCT, the primary outcome will be the progression criteria. The progression criteria use a traffic light system. Green criteria indicate support for progression to a full trial. Amber criteria indicate that a full trial may be possible but some changes may be required and/or consideration given. If neither Green nor Amber criteria are met there may be significant concerns about progressing to a full RCT.

#### Green criteria:

- No serious concerns have arisen about the acceptability of study procedures
- At least 7/8 schools are successfully recruited, randomised and retained throughout the study
- Participation rates at intervention and control schools retained in the trial are at least:
  - 80% of teacher-reported SDQ at baseline. 80% retained at follow-up.
  - 80% of child-report Stirling Wellbeing Questionnaire at baseline. 80% retained at follow-up.
- No marked differences in the characteristics of the children with missing data on teacher report measures when compared to those with complete data.
- Evidence that play has improved at intervention schools, based on at least two of the following: scan observations, focal observations, child-report and school-staff report,
- There is evidence of at least good reliability for scan observations, focal observations and assessment of physical activity.
- Measures used capture range of costs and benefits based on process evaluation and qualitative interviews.

- No serious negative impacts have arisen.

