### Amber criteria (where no amber criteria exist, the green criteria apply):

- At least 6/8 schools are successfully recruited, randomised and retained throughout the study
- Participation rates at intervention and control schools retained in the trial are at least:
  - 60% of teacher-reported SDQ at baseline. 80% retained at follow-up.
  - 60% of child-report Stirling Wellbeing Questionnaire at baseline. 60% retained at follow-up.
- Any differences in the characteristics of the children with missing data on teacher report measures (when compared to those with complete data) are able to be handled successfully via statistical methods.
- There is evidence of at least adequate reliability for scan observations, focal observations and assessment of physical activity.

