Multidimensional Toolkit for the Assessment of Play in Schools (M-TAPS) Scan observations.	During the M-TAPS scan observations, the entire playground is scanned and observers count each: 1) activity type; 2) probability of adventure; 3) affect; 4) physical activity level.  Activity count data will feed into evaluation of changes in play between pre and post-intervention.
Intervention schools only:  Multidimensional Toolkit for the Assessment of Play in Schools (M-TAPS) Focal observations.	A subsample of 40 children from each intervention school (160 total) from Years 1-4 (at baseline) will be observed in focal observations. 20 of these children will have at least 'slightly elevated' (a score of 4 or higher) scores on the SDQ emotional difficulties scale based on parent measures at baseline; 20 will be age and gender matched controls whose scores on the SDQ emotional problems subscale are within the 'Close to average' range.
	Focal playground observations capture activity type, probability of adventure, affect and activity level of each child in the focal subsample.
	All children will be observed twice and then averaged together across days. Reliability assessments will be conducted on approximately 20% of the observations. Intra-class correlation will be used to evaluate reliability of coding.
	The data collected will be used to contribute to the evaluation of how play has changes from baseline to post-intervention (including an evaluation of whether changes are seen for both groups of selected children).
	groupe of colocica crimarony.

Additional measures and information				
Qualitative interviews with children about their experiences of the playtimes (post-intervention only).	Qualitative interviews will be conducted to determine the pros and cons of the play programme from children's perspectives. These will be crucial for determining whether the programme had any unexpected effects on children that were not captured by other measures. It will also provide a more in-depth understanding of the programme from the child's perspective.			

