### 10 STATISTICS AND DATA ANALYSIS

The primary objective is to examine feasibility. The analysis will therefore focus on the following:

- Whether any serious concerns or serious negative impacts have arisen about the acceptability of study procedures or impacts of the intervention. This will be based on informal communication with the schools, formal communication with the schools, as well as the process interviews and qualitative interviews.
- The number of schools who were successfully recruited, randomised and retained throughout the study (including a record of those who were approached but declined or withdrew).
- Participation rates at intervention and control schools for the following measures:
  - 1. teacher-reported SDQ at baseline and post-intervention.
  - 2. child-report Stirling Wellbeing Questionnaire at baseline and follow-up for children in year 3 and 4 at baseline.
  - 3. Comparison using chi-square analysis of those with missing data vs. complete data on teacher report SDQ on demographic characteristics.
- Baseline to post-intervention comparisons of the following measures of children's play:

- 1. scan observations
- 2. focal observations
- 3. child-report
- 4. school-staff report,
- reliability analysis for:
  - 1. scan observations
  - 2. focal observations
  - 3. observation of physical activity.
- Proportion of missing data on measures used capture range of costs and benefits.

In addition, inductive thematic analysis will be used to analyse the qualitative interviews, with a focus on whether the costs and benefits described are captured in the battery of questionnaires and observation.

Inductive thematic analysis will be used to conduct the process evaluation, once transcribing and coding are complete.

As this is a feasibility study, significance tests will not be performed. Intervention effects will be represented by point estimates and their standard deviations. Point estimates will be calculated by subtracting unadjusted mean data at post-intervention from the mean data at baseline. These will be used along with their standard deviations to inform sample size calculations for a definitive trial, if appropriate.

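### The progression criterion on improved play is judged by change over time at intervention schools alone, although three of its four sources are also measured at randomised control schools

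*Protocol*

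**What the plan says.** Protocol Section 3.4 gives the criterion its weight: "For the feasibility RCT, the primary outcome will be the progression criteria". One of the Green criteria, repeated in the Trial Summary, is "Evidence that play has improved at intervention schools, based on at least two of the following", the four sources being scan observations, focal observations, child report and staff report. Section 3.4 lists no separate Amber version, and its Amber heading reads "Amber criteria (where no amber criteria exist, the green criteria apply", so the same rule governs Amber.

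Section 10 describes the analysis as "Baseline to post-intervention comparisons of the following measures of children's play", followed by the same four sources. It adds: "As this is a feasibility study, significance tests will not be performed". Intervention effects there are differences between unadjusted baseline and post-intervention means, reported with standard deviations. No control term appears.

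Other sections show what data will exist:
- Section 7.3.1 allocates schools 1:1 in four blocks of two, giving four schools per arm.
- Section 7 has follow-up data collected at all intervention and control schools still in the trial. Section 7.7 repeats the baseline measures, with exceptions that do not touch the play measures.
- Among the play measures in Section 7.6, only the focal observations are confined to intervention schools.
- Section 7.7 estimates baseline at January to July 2024 and post-intervention at November 2025 to May 2026.

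**The concern.** This is the only progression criterion that asks whether play changed, and Section 7.6 names play as the route by which the programme would act on mental health. A before-and-after change in one arm mixes any OPAL effect with everything else that changed in the interval. The trial randomises schools and measures three of the four sources in both arms, so it could remove much of that mixture, but the criterion does not use the comparison.

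The risk runs both ways. Favourable drift could credit an inert programme with changing play. Adverse drift could hide a real improvement and count against a full trial. Unlike the school-retention and participation criteria, this one carries no figure in the protocol, and no score within any source is named as decisive.

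**Working it through.** **1. Is control data available?** Taking Sections 7, 7.6 and 7.7 together: scan observations, yes; child report, yes; staff report, yes; focal observations, no. A between-arm contrast is possible for three of four sources without new data.

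**2. What changes with time?**
- Season: January 2024 to November 2025 is 22 months, and July 2024 to May 2026 is also 22 months. The follow-up window therefore opens and closes two calendar months earlier in the year than the baseline window. The protocol does not say which way this moves outdoor play.
- Age: child questionnaires cover Years 3 and 4 at baseline (Section 7.2). The windows lie in school years 2023/24 and 2025/26, so these children are then two year groups higher. This does not readily apply to scan observations, which count the whole playground.
- Reporting: Section 7.4 says participants cannot be blind and observer blinding cannot be guaranteed; focal observers are unblinded. A control contrast does not remove bias from knowing the allocation.

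**3. Illustrative pass rate with no OPAL effect.** The protocol gives no figure to reproduce. Assume that any favourable point change counts as improvement, with one score per source. Let p be the chance that a source moves favourably. For independent sources,

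P(at least 2 of 4) = 1 − (1−p)^4 − 4p(1−p)^3.

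With no drift p = 0.5, so P = 1 − 1/16 − 4/16 = 11/16 = 0.69. By simulation with equally correlated normal changes, P is 0.63 at correlation 0.3, 0.60 at 0.5 and 0.56 at 0.8.

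**4. Adding drift.** If time alone shifts every source by d standard errors of its change, p = Φ(d). For independent sources:

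| Drift d (SE) | p | P(at least 2 of 4) |
|---|---|---|
| −1 | 0.159 | 0.12 |
| −0.5 | 0.309 | 0.36 |
| 0 | 0.500 | 0.69 |
| +0.5 | 0.691 | 0.91 |
| +1 | 0.841 | 0.99 |

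**5. Effect of a stricter reading.** For independent sources without drift, P falls below 0.5 once the per-source false-positive rate is below about 0.39. At 0.20 it is 0.18; at 0.10 it is 0.05.

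**6. Would a control contrast alone be enough?** Counted by sign on two of three sources with no effect, P = 3(0.5)^2(0.5) + (0.5)^3 = 0.50. It removes drift common to both arms but leaves a coin toss, so a minimum difference is needed too. With a per-source false-positive rate of 0.20, two of three gives 3(0.04)(0.8) + 0.008 = 0.104. At 0.10 it gives 3(0.01)(0.9) + 0.001 = 0.028.

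**7. What can four schools per arm show?** Measure the effect in between-school SDs of the adjusted score (an assumption). The standard error is √(1/4 + 1/4) = 0.71 SD. With 6 degrees of freedom an 80% interval has half-width 1.44 × 0.71 = 1.02 SD. If that interval had to exclude zero favourably, a true effect of 1 SD would pass a given source about 51% of the time, and two of three independent sources 3(0.51)^2(0.49) + (0.51)^3 ≈ 0.52.

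**The case against.** The strongest reply is that the pass rates depend on a reading the protocol does not fix. The criterion asks for evidence, not for any increase. Excluding significance tests does not stop the team from weighing the size of a change against its standard deviation. A statistical analysis plan that is not shown may set a cut-off and name the deciding scores. A reader might infer that the criterion is more likely than not to be met when OPAL does nothing. The documents do not support that as a general statement: it needs a sign-only reading and no material adverse drift, and it reverses under a moderately strict rule (step 5). This part of the reply stands.

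A reader might also expect drift to favour a pass. Nothing in the protocol says so, and follow-up is placed nearer to winter. Regression to the mean in the focal sample is a further tempting argument, but a weak one: those children are selected on parent-rated SDQ, not on play, and Section 7.6 already plans to look at change in both selected groups.

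The criterion is also one of several. Section 3.4 says that Green only indicates support for a full trial, Section 3.1 evaluates no hypotheses, and interviews inform the decision as well. It could not send a programme forward by itself.

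None of this answers the central point. The restriction to intervention schools is in the criterion's own wording, and the before-and-after comparison is in Section 10. A cut-off added elsewhere would not turn uncontrolled change into a comparison with control schools.

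**Conclusion.** The concern holds in a conditional form. The protocol fixes this part of the primary outcome, for Green and Amber alike, as uncontrolled change at intervention schools, while randomised control data exist for three of the four sources. Followed as written, the rule cannot separate an OPAL effect from changes in season, age or other time trends.

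The size cannot be fixed from the documents. With no effect, no drift and a sign-only reading, the pass rate is about 69% for independent sources and about 60% at correlation 0.5. With independent sources it ranges from about 36% to 91% as drift goes from −0.5 to +0.5 standard errors. That spread matters more than any single figure, because it shows how strongly time effects could decide the result. The absence of a cut-off and of a deciding score is a secondary point that an analysis plan may settle. This is a should-fix.

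**What to change.** In the Trial Summary, Section 3.4 and Section 10:
- Judge the criterion on the intervention-minus-control difference, in baseline-adjusted follow-up or in change, for scan observations, child report and staff report. Require a favourable result on two of these three.
- Name one score per source and its favourable direction. Section 10 words the point estimate as baseline minus post-intervention, so a rise would appear as a negative number.
- Set a minimum favourable difference for each score before follow-up data are seen.
- Report the estimates descriptively with intervals that respect the school as the unit. Making an interval exclude zero would in effect be a significance test and would sit badly with Section 10.
- Keep focal observations, which have no control arm, as supporting evidence.

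The cost is rewording; no new data are needed. The downside is precision: with four schools per arm a strict bar would often miss a real change (step 7), so the bar should be modest and its precision stated beside it. The contrast also leaves reporting bias from unblinded participants, which should be acknowledged when the result is read.
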